**Specify:**

**5 How often will data and safety monitoring be performed? Please specify if this is a specific number of times, at defined time points, after a certain number of subjects have been recruited or as needed (i.e. every 6 months, every SAE, every 5 subjects, etc.). If this information is in protocol, please specify where relevant information is located.**

As every 3rd subject is enrolled, or as needed/immediately for any serious adverse event.

**6 Describe the responsibilities that have been given to the data and safety monitoring function. This should include a discussion of whether the data and safety monitoring plan includes a charter, whether stopping rules will be developed, and if any interim analysis will be performed (if so, on what basis). If this information is in protocol, please specify where relevant information is located.**

Risks of this study are low, but greater than minimal risk, due to the fact that the medications to be used have minimal potential side effects and will be given in traditionally accepted/clinically utilized doses

Given that this is a small pilot study with somewhat subjective outcomes, aggregate unblinded data will not be reviewed by the DSMB for fear of introducing bias. Potential side effects of the medications will be reviewed at each study visit by the research coordinator, and laboratory data obtained, looking for any significant safety issues. Any concerns regarding side effects of the medication, or any laboratory values outside of the expected range, will be brought to the attention of the PI by the research coordinator immediately.

**7 If this protocol is for a multicenter trial what mechanisms are in place to either receive or distribute results of the data and safety monitoring function in a prompt manner.**

The protocol will be conducted at BWH and CHB. The same investigator group is overseeing and running the trial at both institutions, so dissemination of data and results will be seamless. The monitoring group will have access to all data, regardless of at which institution the subject is seen.

**8 If a DSM charter exists, please upload it.**

[name] Monitoring Plan.Signed.03.31.17.pdf	3/31/2017 11:58 AM	0.02	[name]
MONITORING SOP.Signed.03.31.17.pdf	3/31/2017 11:58 AM	0.02	[name]

**Risks and Benefits****Risks**

- 1 **\* Provide a description of the foreseeable risks to subjects. Consider all types of risks, including physical, psychological, social/reputation, legal, financial, privacy and breach of a promise of confidentiality.**

The potential risks and discomforts include a bruise at the site of venipuncture (for subjects electing to provide a blood sample); infection resulting from venipuncture is also a risk, albeit very rare. Subjects may also experience discomfort when asked sensitive questions about their lifestyle as part of the questionnaire.

Another potential risk to participation would be a breach of confidentiality. In order to minimize this risk, all samples are stored with a code number unique to each participant. Samples will not be labeled with any type of identifying information such as name or medical record number. All health information is also de-identified, and labeled only with the code number. All data are kept in a secured server, in files that are password protected. Only authorized personnel within the Boston Center for Endometriosis will have access to identifying information. If samples are shared with researchers, they will be identified only by the unique code number and possibly by non-identifying information such as age, race, or ethnicity. Samples will not be sold for profit. If results of tests performed on the specimens are ever published in the medical literature, no identifying information will be included. The results of the tests performed for research purposes will not be placed in the medical record. A copy of the consent form will not be placed in the medical record. In this manner it will be unlikely that others within the hospital, an insurance company or employer would ever learn of such results.

Risks of the medications to be given in this study are low when eligibility criteria are met, as described below:

Norethindrone acetate is a synthetic hormone, which will be given to subjects at physiological doses. Thus, we do not anticipate adverse events associated with use of the medication. In the numerous studies of adult women with endometriosis to whom norethindrone acetate was given, no significant adverse events were reported. Side effects could include: weight changes, edema, acne, headache, or change in mood. We will assess for these side effects with repeated physical examinations and the self-administered assessments, the SF-36, Beck Depression Inventory, the pain measures, and the MRS.

The safety of cabergoline has been evaluated in approximately 1,200 patients with Parkinson's disease in controlled and uncontrolled studies at dosages of up to 11.5 mg/day which greatly exceeds the maximum recommended dosage of cabergoline for hyperprolactinemic disorders, and the dosage used in the proposed pilot study. When used in similar populations of reproductive aged women for other indications, at doses identical to those proposed in the current study, cabergoline side effects include: GI distress (constipation, pain), dizziness, headache, tingling, or swelling of the extremities. In addition to the adverse events that occurred in the patients with hyperprolactinemic disorders, the most common adverse events in patients with Parkinson's disease (and treated with doses of ~3 mg/day) were dyskinesia, hallucinations, confusion, and peripheral edema. Heart failure, pleural effusion, pulmonary fibrosis, and gastric or duodenal ulcer occurred rarely. Postmarketing cases of cardiac valvulopathy have been reported in patients receiving cabergoline. These cases have generally occurred during administration of high doses of cabergoline (>2mg/day) for the treatment of Parkinson's disease. No significantly increased risk of clinically relevant cardiac valve disorders was found in subjects treated with long-term cabergoline therapy at the doses used in endocrine practice. Current expert recommendations state that patients prescribed cabergoline should be screened by a clinical cardiovascular examination and that echocardiogram should be reserved for those patients with an audible murmur, those treated for more than 5 years at a dose of more than 3 mg per week, or those who maintain cabergoline treatment after the age of 50 years.

Erythrocyte sedimentation rate (ESR) has been found to be abnormally increased in association with pleural effusion/fibrosis. We will utilize a measurement of ESR at each study visit to screen for the very unlikely development of a fibrotic disorder associated with low-dose cabergoline use. If we find that the ESR increases to abnormal levels, a clinical evaluation would be indicated, including a chest x-ray. Serum creatinine measurements can also be used to help in the diagnosis of fibrotic disorder, and will be checked at each visit.

The effects of the study drugs on the reproductive system (sperm, eggs) or to the developing fetus are not well understood. Norethindrone acetate is labeled by the drug manufacturer as "contraindicated during pregnancy". Of note, norethindrone (another first generation progestin) 0.35 mg PO daily is FDA approved and marketed as an effective method of birth control. In our study, patients randomized to

norethindrone acetate will receive 5 mg po daily. Cabergoline has no known effect on pregnancy, based upon animal reproductive studies, and is approved for use during pregnancy "if needed". For these reasons, a pregnancy test will be performed at each visit. Women who become pregnant during the study would be terminated from further study participation. For this reason, participants taking the drug should not become pregnant. To be a part of the research, participants will be advised that they must not have sexual intercourse or must use reliable, effective birth control during participation.

During research visits, participants may be asked questions that lead to feelings of discomfort, emotional upset, or frustration. Participants will be advised that they may not be able to answer all the questions and do not need to answer any questions that they do not wish to answer. If the participant were to become distressed, the Principal Investigator will be notified by the Research Coordinator. We will offer to have the participant speak to a mental health professional regarding her feelings. The Beck Depression Inventory-II will be scored by the Research Coordinator during the study visit, while the participant is still present. It is possible that the study team could identify concerns for depression from the answers to the questionnaires. If the participant has a score  $\geq 20$  (indicating moderate or severe depression) or responds anything other than 0 to Item 9 (I don't have any thoughts of killing myself), the Research Coordinator will alert the Principal Investigator immediately. The study team will notify the participant regarding our findings from the Depression Inventory, and encourage the participant to allow us to share the information with her parent (if she is age < 18 years) or her healthcare provider. Additionally, mental health resources will be made available to the participant. Participants are informed within the consent form that "If, during your participation in this research, there is reason to believe that you are at risk for being suicidal or otherwise harming yourself or others, the research team is required by law and Hospital policy to act on this suspicion. This may include notifying your parent (if you are age < 18), your therapist(s) if applicable, or other individuals. If you are

**2 \* What is the likelihood and seriousness of such risks?**

The likelihood of such risks is low, and no serious risks are anticipated.

**3 \* Describe provisions for minimizing risks to participants.**

Subjects are monitored closely throughout the course of participation by both the study team, and with their clinical care gynecology provider.

At the baseline study visit, we will measure blood samples for total cholesterol, HDL cholesterol, and triglyceride levels. This lipid profile will allow us to monitor for any individual changes in serum lipids from baseline, and for differences between treatment groups. In some studies of adult women, mildly deleterious effects on circulating lipid profiles have been seen in patients receiving treatment with norethindrone acetate (decreased HDL). Lipid profiles will be repeated at follow-up visits scheduled for 3 and 6 months after initiation of therapy. Blood samples will also be taken for liver function tests (AST, ALT) at each visit to allow us to monitor for any liver inflammation associated with the drug therapy. HbA1c will be taken at baseline and at 6 months to monitor for impairments in glucose metabolism. We will utilize a measurement of ESR and serum creatinine at each study visit to screen for the very unlikely development of a fibrotic disorder associated with low-dose cabergoline use. A physical examination will be performed at each visit to assess for acne, and cardiac auscultation will be done to assess for the presence of a cardiac murmur. The presence or absence of hormonal symptoms (mood changes, breast tenderness, acne, and changes in menstrual bleeding patterns) will be queried at each visit. The hormonal milieu will be assessed using serum measurements of estradiol and prolactin at baseline and each subsequent study visit. These laboratory studies will allow us to monitor cabergoline activity, and to determine compliance with cabergoline treatment in Group 2. If any cardiac murmur is identified during study participation, an echocardiogram will be performed.

Subjects will be discontinued from further study participation if any of the conditions that are listed as exclusion criteria for participation develop during the six months of active participation in the study. Because of the potential risk of adverse side effects, patients in the treatment trial will be monitored closely during the 6-month study period with laboratory assessments and physical examinations every three months.

Study participants will be able to contact one of the study physicians at any time if questions or concerns arise. No confidential information from this study or other data within a patient's medical record may be furnished to anyone unaffiliated with Children's Hospital without written consent, except as required by law or regulatory agencies (e.g., FDA).

All participants will be advised to abstain from sexual intercourse, or to use reliable birth control to prevent pregnancy. A pregnancy test will be performed at each of the 3 study visits.

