**2.2.1 What types of results will you provide? How will you provide the results? When will you provide the result?**

Subjects will have access to their clinically relevant laboratory results, such as lipid labs. These results will be provided to the patient within 1-2 weeks after each study visit.

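### Post-baseline prolactin and estradiol results are informative about the arm, but the supplied text does not keep them from participants or blinded investigators before the month-6 BPI

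*Protocol*

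**What the plan says.** **The blind.** Protocol, Placebo, item 1: each participant takes one daily and one twice-weekly pill, so that neither she nor the investigators know her group.

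**The hormone assays.** Protocol, Risks and Benefits, item 3: estradiol and prolactin are measured at baseline and at every later visit. The next sentence gives the purpose: "These laboratory studies will allow us to monitor cabergoline activity, and to determine compliance with cabergoline treatment in Group 2".

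**Return to participants.** Potential Benefits, item 4.1, and Pediatric Risk/Benefit Determination, item 1.1.1, both list hormonal status among the results that participants receive. Neither says when. Dissemination of Non-Genetic Results, item 2.2.1, gives the only timing: "Subjects will have access to their clinically relevant laboratory results, such as lipid labs", and "These results will be provided to the patient within 1-2 weeks after each study visit". It names lipids and no hormone.

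**Escalation.** Data and Safety Monitoring, item 6: "any laboratory values outside of the expected range, will be brought to the attention of the PI by the research coordinator immediately". The expected range is not defined, and no assay is excepted.

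**Safeguards.** The same item states that "aggregate unblinded data will not be reviewed by the DSMB for fear of introducing bias". Dissemination of Aggregate Results, item 3.2, holds aggregate results until the trial has been completed and analyzed. Risks and Benefits, item 1, keeps research test results out of the medical record.

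**The outcome.** SAP, Statistical Plan: the primary comparison is change in BPI pain score, with group differences estimated at each time point and used to plan a later trial. Data and Safety Monitoring, item 6, acknowledges that the outcomes are to some degree subjective.

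**The concern.** A double dummy hides the pills, not what the drugs do to a blood test. If a test is good enough to show whether someone is taking cabergoline, whoever sees its result may be able to infer the arm. The plan recognizes this kind of risk when it keeps unblinded summaries from the DSMB, but it does not extend the protection to a single participant's values.

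At stake is the month-6 BPI. A participant who believes she knows her treatment, or who is in contact with an investigator who believes so, may rate her pain differently. That rating enters the estimates that the SAP will carry into the design of the next trial.

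**Working it through.** The plan gives no figure on this point. Its one sample-size calculation (5 completers / 0.80 = 6.25, rounded up to 7 per arm, 14 in total) reproduces and is not affected. The check is mainly a reading of the passages against each other.

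**1. Are the hormone results informative about the arm?** By the plan's own account, yes, as a pair: Risks and Benefits, item 3, uses them to detect cabergoline activity and compliance. The off-label section of the Protocol gives hyperprolactinemia as cabergoline's labelled indication, which fits prolactin being the more telling marker. No direction is stated for estradiol alone.

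**2. Which results exist before the last BPI?** Blood Collections, item 3, gives draws at baseline, 3 and 6 months. Privacy and Confidentiality, item 1, has questionnaires completed during research visits. That the BPI is taken at months 3 and 6 is inferred from this schedule and from the SAP's contrasts at each time point.
- Baseline draw: before treatment, so it says nothing about the arm.
- Month-3 draw: on treatment. The month-3 BPI belongs to the same visit, before results come back, so it is not exposed.
- Month-6 draw: belongs to the visit of the last BPI, so its result comes too late to matter.

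One on-treatment result set (month 3) can therefore precede a later rating, and one of the two post-baseline ratings (month 6) is exposed.

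**3. How early could a month-3 result arrive?** Three months is 52/4 = 13 weeks. Under the 1-2 week return rule it arrives 13 - 1 = 12 to 13 - 2 = 11 weeks before the month-6 BPI. This applies to hormones only if that rule covers them, which the text does not settle. Escalation to the PI would be immediate.

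**4. Do the stated rules let hormone values through?**

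| Route | What is stated | What is not stated |
|---|---|---|
| To the participant | Hormonal status is among the results she is given | When |
| To the PI | Any out-of-range laboratory value, at once | The range; any exception for hormones |

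**5. Does any safeguard close these routes?** The DSMB rule and the aggregate-results rule concern summaries. The medical-record rule concerns where results are filed. None addresses a participant, the coordinator or the PI seeing one participant's value.

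**6. How large could the bias be?** Let a be the probability that the arm is guessed correctly, and b the shift in reported BPI caused by believing in one arm rather than the other. The group contrast then moves by a x b - (1 - a) x b = (2a - 1) x b. This is zero if the guess is no better than chance (a = 0.5) or if belief does not change ratings (b = 0). The documents give neither a nor b, so no size is computed.

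**The case against.** **The markers and the routes do not line up.** The only return with a stated time names lipids, while the more informative results are the hormones, whose return has no stated time. This is correct, and it is why the point is that hormone results could arrive before month 6, not that they will.

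**The compliance check could be run after unblinding.** Risks and Benefits, item 3, does not say when or by whom it is done, so that sentence alone does not contradict the Placebo section. This also stands. The difficulty arises only when it is read with the return and escalation rules.

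**The supplied text is an IRB form.** The protocol upload (Protocol and Appendices, item 1), the monitoring plan and SOP (Data and Safety Monitoring, item 8) and the test results letter (Protocol and Appendices, item 2.3) were not available. Any of them could contain a masking rule. The finding is therefore that masking is not stated here.

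**Side effects and bleeding changes may hint at the arm anyway.** They may, and the fix does not remove them. That is no reason to add a clue that wording can remove.

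A reader might go further in three ways that the documents do not support:
- *Lipid results unblind participants and must be held back.* Risks and Benefits, item 3, describes lower HDL on norethindrone acetate as a mild effect seen in some adult studies. One participant's HDL is a weak clue. Lipids are also safety tests, and their return is part of the benefit case for minors.
- *Safety-monitoring co-investigators will see individual hormone values.* This rests on a tick-box state that cannot be read with certainty from the converted text, and on an unclear reference to the monitoring group.
- *Staff who see the results also rate the primary outcome.* The coordinator scores the Beck inventory, but nothing shows staff scoring the BPI, and Risks and Benefits, item 1, groups the pain measures with self-administered assessments.

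**Conclusion.** The point holds as a should-fix, with medium confidence. Followed as written, the return and escalation rules can pass hormone results that the plan itself treats as arm-informative to people it says are blinded, before the month-6 self-report. No stated safeguard covers this. The exposure is one result set (month 3) ahead of one of the two post-baseline BPI ratings. The bias has no derivable size and may be zero.

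The text does not show that the blind would fail or that the month-6 estimate would be biased, and it would be wrong to infer either. The conclusion assumes that the BPI is completed at months 3 and 6, that hormonal status includes prolactin and estradiol, and that the documents not supplied contain no masking rule. No sample-size figure changes.

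**What to change.** Make the same statement in Data and Safety Monitoring, item 6; Risks and Benefits, item 3; Potential Benefits, item 4.1; Pediatric Risk/Benefit Determination, item 1.1.1; and Dissemination of Non-Genetic Results, item 2.2.1:

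- Post-baseline prolactin and estradiol values are not released to the participant or to blinded study staff until her month-6 BPI is complete.
- The independent monitor named in Data and Safety Monitoring, item 3, receives them by study ID. The sponsor should confirm that this person has no part in participant contact or outcome assessment.
- The Group 2 compliance analysis is run after unblinding.

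The sponsor must also reconcile the escalation of out-of-range hormone values with the Placebo section so that safety escalation is preserved. No clinical rule is proposed here. The sponsor should likewise consider how the return of lipid results sits with the blind, as a weak possible clue only. If a masking rule already exists in the uploaded documents, citing it in these five places is enough.

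**Cost.** Wording in five places and one routing instruction for month-3 results. Participants may receive hormone results later, and the independent monitor has slightly more work. The IRB must see the change, because hormonal status is listed in the pediatric risk/benefit justification. The consent form must match wherever it describes the return of results.

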**Potential Benefits**

**4 \* Are there potential direct benefits to the research participants?**

Yes  No

If YES:

**4.1 Describe the potential direct benefits to the research participants.**

The medications used will be provided to the patient at no cost, and will potentially ameliorate

ongoing endometriosis-associated pain. Participants will be given information about their results to share with their primary care provider, including monitoring of lipid panels, liver function, and hormonal status.

**5 \* Describe how the research may result in knowledge expected to benefit society.**

With the information gathered from the proposed study, we hope to develop evidence-based guidelines for the utilization of norethindrone acetate and/or cabergoline for treatment of endometriosis. This study has the potential to benefit a large number of patients who suffer from endometriosis.

## Pediatric Risk/Benefit Determination

*All protocols that include children/adolescents must be classified into a risk/benefit category.*

*Does your study involve more than one risk/benefit category for different groups? If so, answer questions 1, 1.1, 1.2 and 1.3 to describe the least favorable risk/benefit scenario, and use the questions 2, 2.1, 2.2, 2.3, 2.4 to explain the risk/benefit assessment for the other groups of subjects in your study.*

*“Minimal risk” means that the probability and magnitude of harm or discomfort anticipated in the research are not greater in and of themselves than those ordinarily encountered in daily life or during the performance of routine physical or psychological examinations or tests.*

**1 \* Check the category below that best represents the degree of risk and benefit which children in this study will be exposed to. If your study involves more than one group of subjects ( eg. .experimental and placebo groups) consider whether the research presents a different risk/benefit assessment for each group. If this is the case select the least favorable risk/benefit ratio that might apply to any of the subjects.**

For example, a study may present greater than minimal risk with potential for direct benefit for an experimental group, but no potential for direct benefit for a placebo group. In this case you should select “Greater than Minimal Risk; No Potential for Direct Benefit” in this section and use section 2 below to describe the risks and benefits for the group for which there a potential for benefit.

- No more than Minimal Risk; Potential for Direct Benefit
- No more than Minimal Risk; No Potential for Direct Benefit
- Greater than Minimal Risk; Potential for Direct Benefit**
- Greater than Minimal Risk; No Potential for Direct Benefit, but likely to yield generalizable knowledge about the subject's condition

